9.3.2 Day 8 ±3 Days

- Vital signs and weight.
- Pregnancy test for FCBP required for Cycle 1 only).
- Clinical laboratory tests: hematology, serum chemistry.
- POM administration (Days 1 -21).
- DEX administration (Days 1, 8, 15 and 22).
- AE and SAE monitoring. Concomitant medication assessment.

9.3.3 Day 15 ±3 Days

- Vital signs and weight.
- Pregnancy test for FCPB (required for Cycle 1) then if applicable for subsequent cycles.
- Clinical laboratory tests: hematology, serum chemistry (including albumin).
- POM administration (Days 1 -21).
- DEX (Days 1, 8, 15 and 22).
- AE and SAE monitoring. Concomitant medication assessment.

9.3.4 Day 22 ±3 Days

- Vital signs and weight.
- Pregnancy test for FCBP (required for Cycle 1 only).
- Clinical laboratory tests: hematology serum chemistry.
- DEX administration (Days 1, 8, 15 and 22).
- AE and SAE monitoring.
- Concomitant medication assessment.

9.3.5 Cycle Delay

- If a cycle is delayed, end of cycle evaluation for toxicity resolution if required Day 28 ± 3 days, then Every 7 ± 3 days.
- Concomitant medication assessment.
- ECOG performance status.
- Vital signs and weight.
- Clinical laboratory tests: hematology, serum chemistry (including albumin).
- AE and SAE monitoring.

9.4 Additional Cycles

 In the event that patients are permitted to continue therapy beyond 6 cycles, the same study procedures as during Cycles 1 – 6 will be followed.

9.5 End of Treatment

- Physical examination.
- ECOG performance status.
- Vital signs and weight.
- 12-lead ECG.
- Pregnancy test.
- Clinical laboratory tests: hematology, serum electrolytes, and chemistry (including albumin).

- PT or INR/aPTT.
- Urinalysis.
- Extramedullary disease evaluation,
- BM aspiration.
- Collection of peripheral blood (whole blood, serum, plasma) for correlative studies.
- MM-specific laboratory tests.
- Collection of peripheral blood for PK sampling.
- Collection of peripheral blood (serum) for immunogenicity.
- AE and SAE monitoring.
- Concomitant medication assessment.

9.6 Safety Monitoring: Through 30 days after Last Infusion

- AE and SAE monitoring.
- Survival status.
- Concomitant medications.
- Myeloma-specific laboratory tests.
- Skeletal survey.
- Extramedullary disease evaluation.

9.7 Follow-Up

Patients who discontinue therapy for reasons other than MM progression will be followed for disease response every month until progression of disease or initiation of subsequent therapy. Patients who have discontinued study therapy and have had MM progression should be contacted approximately every 3 months (telephone contact is permitted) to assess survival status for up to one year; patients who discontinue therapy for reasons other than disease progression and are no longer willing to follow-up for evaluation of disease progression should also be contacted for survival status whenever feasible.

Table 13: Schedule of Events

	Screening/ Baseline	Run in Cycle Cycle is 28 days																	
Evaluation	D-21 to -1	D 1	D 2	D 3	D 4	D 5	D 8	D 15	D 22	D 1	D 2	D 3	D 4	D 5	D 8	D 15	D 22	EOT	F/Uw
Informed Consent & Pomalyst REMS ^a	х																		
Entry Criteria Review	Х											,							
Medical and Myeloma History	x																		
Physical Examination ^c	X	X	Х	Х	Х	Х	X	Х	Х	х	X	Х	Х	Х	Х	X	Х	X	
Performance Status (ECOG)	х	x								х								x	
Height (Baseline only) / Weight	х	x	х	х	х	х	x	х	х	х	х	х	х	х	х	х	х	х	
Vital Signs (HR, Temperature, RR, $\mathrm{BP})^{\mathrm{d}}$	x	X	x	х	х	х	x	x		х	х	x	x	x	x	x		x	
ECG	X									х								х	
ECHO/MUGA	х								77										
Pregnancy testing [FCBP) and counseling *	х								Xe	х					Xe	Xe	Xe	х	
Hematology	X	x	x	х	х	х	x	x	x	Xf	x	х	х	x	х	x	х	x	
Serum Chemistry®	X	X	X	Х	х	X	X	X	X	Х	х	Х	X	Х	X	X	Х	X	
PT / INR aPTT	х									х								x	
Urinalysis h	Х	X								х								х	
Plasmacytoma Evaluation ⁱ	x									Xi								x	As needed
Skeletal Survey j	X																		As needed
Bone Marrow Aspiration and biopsy ^k	х									Xk								х	
Peripheral blood for correlative studies ¹	x									Xl								x	

	Screening/ Baseline				Run ir ycle is					Cycles 1 - 6 ⁿ Each Cycle is 28 days									
Evaluation	D-21 to -1	D 1	D 2	D 3	D 4	D 5	D 8	D 15	D 22	D 1	D 2	D 3	D 4	D 5	D 8	D 15	D 22	ЕОТ	F/U ^w
Myeloma-specific Laboratory Tests ^m	x	х								х								х	As needed
PK (SL-401) ⁿ		Х				х				X C2				X C2				x	
Immunogenicity (SL-401)°		x				х				х								x	
SL-401 Pre-medication ^p		x	x	x	x	x				x	x	x	x	x					
SL-401 Administration ^q		х	X	Х	Х	Х				Х	X	х	х	Х					
Pomalidomide ^r										Days 1 - 21									
Dexamethasone										x					x	x	x		
Adverse Event monitoring ⁶	x		← X →							x									
Prior/Concomitant Medication ^t	x			← X →							x								

- Informed consent All patients must sign an IRB approved informed consent prior to screening and agree to enroll in the Pomalyst REMS program prior to starting POM.
- b. Medical History: Includes relevant history of previous/associated pathologies other than the tumor. Myeloma History: Includes date of initial diagnosis, stage, and extent of the disease both at diagnosis and at study entry, previous anti-tumor therapy (including surgical, radiation and systemic therapy; for systemic therapy, includes approximate dates of administration, best response and approximate dates of disease progression).
- c. Physical Examination: Consists of examination of major body systems including neurologic, digestive, respiratory, any evaluable sites of extramedullary disease. Physical examination is required at screening/baseline and Day 1 of each treatment cycle. Symptom directed physical examination may also be performed on other treatment days or mid-cycle evaluations if there are symptoms or vital sign abnormalities warranting examination.
- d. Vitals signs: HR, temperature, RR, BP, and pulse oximetry to be taken pre- SL-401 infusion, end of SL-401 infusion, every 30 minutes for 4 hours post end of infusion and as clinically indicated for all doses of the Run-in Cycle. Cycle 1 +, vital signs are to be taken pre-infusion, at end of infusion and as clinically indicated. For temperature ≥ 38°C, draw blood cultures ×2 and collect urine for urinalysis and culture.
- e. **Pregnancy tests** for FCBP at screening, test must be repeated within 10 14 days prior to initiation of POM therapy (before Cycle 1) and again within 24 hours prior to initiation of POM therapy (before Cycle 1). While on POM, repeat pregnancy test every week for the first 4 weeks and then every 28 days while on therapy and during interruptions in therapy and 28 days following discontinuation of POM. Women with irregular menstruation must have pregnancy testing every 14 days while on therapy and during interruptions and 14 and 28 days after discontinuation of POM. All patients enrolled into this study, must be registered in and must comply with all requirements of the POMALYST REMSTM program. A FCBP is a female of childbearing potential is a sexually mature woman who: 1) has not undergone a hysterectomy or bilateral opphorectomy; or 2) has not been naturally postmenopausal for at least 24 consecutive months.
- Hematology: CBC to be performed and reviewed by clinician prior to SL-401 dosing on Days 1 5 and Days 8, 15 and 22 or as clinically indicated. The Run in and Cycle
 1, Day 1, results must remain within the entry criteria values to initiate therapy.
- g. Serum Chemistry: to be performed and reviewed by clinician prior to SL-401 dosing on Days 1 5 and Days 8, 15, and 22 or as clinically indicated. The Run in and Cycle 1 Day 1 results must remain within the entry criteria values to initiate therapy. Chemistry includes: glucose (fasting at baseline), albumin, total protein, AST, ALT, bilirubin

- (total and direct), alkaline phosphatase, LDH, CPK, sodium, potassium, chloride, bicarbonate/carbon dioxide, calcium, magnesium, phosphate, uric acid, BUN, serum creatinine and estimated creatinine clearance (Cockroft-Gault formula Appendix 15.7). Albumin, transaminases (AST/ALT) and creatinine must be evaluated prior to each SL-401 dose.
- Urinalysis: Appearance, color, pH, specific gravity, ketones, leukocytes, protein, glucose, bilirubin, urobilinogen, and occult blood. To be performed at baseline, during the treatment period as clinically indicated and EOT.
- i. Plasmacytoma Assessment Disease: For patient with known or suspected plasmacytomas, assess by physical exam and/or radiologic evaluation at baseline and as clinically indicated. Disease that can be assessed by physical exam should be evaluated on Day 1 of each cycle. Disease that can be assessed by radiologic evaluation should be assessed according the IMWG criteria for evaluation of response. This may include computerized tomography (CT) scan, ultrasound, PET/CT or MRI. The same method of assessment should be used at each evaluation for any individual patient. Assess the need to evaluate for suspected new, worsening, or improved plasmacytomas to confirm response or progression every cycle. Evaluations may be performed on Day 1 of a cycle or during the 7 days prior to Day 1 of the Cycle as needed for scheduling.
- j. Skeletal Survey: Plain film X-rays to including skull, vertebrae, all long bones, pelvis and chest are required. PET/CT MRI may be done to supplement X-rays of any disease site at Investigators discretion. Also required at any time when clinically indicated, for suspected progression per IMWG response criteria.
- k. Bone Marrow Aspiration: Bone marrow aspiration for cytogenetic analysis both by FISH and standard karyotyping, and morphologic evaluation including assessment of plasma cell percentage is required at screening/baseline (within 21 days prior to study drug administration. Bone marrow aspirate should be repeated if CR or stringent complete response (sCR) is suspected to confirm achievement of response according to IMWG criteria, and at End of therapy. Additional BM aspirate material (10-15cc if feasible) and biopsy for correlative studies are to be collected at baseline and any time a specimen is obtained to confirm response.
- Peripheral blood for correlative studies should be obtained at baseline, for phase 1 Day 1 of Cycles 1, 3, and 5 and for phase 2 on Day 1 of Cycles 2, 4, and 6 and at EOT for all patients. Four 10 mL tubes in total (3 green top, 1 red top/serum separator tube). Whole blood will be evaluated for circulating MM/plasma cells (and other mononuclear cells of interest); serum and plasma will be for evaluated for potentially relevant circulating cytokines, and surrogate markers of osteolytic activity.
- m. Myeloma-specific laboratory tests: β2 Microglobulin (at baseline only), serum and 24-hour urine immunoelectrophoresis, serum immunoglobulin assay, serum/urine immunofixation and serum FLC with kappa/lambda ratio to be performed at baseline, every cycle prior to study drug administration thereafter and at end of treatment (if last tests were > 4 weeks) and for patients who discontinue therapy for reasons other than disease progression. Myeloma laboratory tests will be repeated every month until disease progression or initiation of subsequent therapy. Response assessment will be done at the beginning of every cycle. Following pre-treatment evaluations on Day 1 of the first cycle evaluations may be performed on Day 1 of a subsequent cycle or during the 7 days prior to Day 1 of the Cycle as needed for scheduling. (Note that an evaluation performed during the final week of Cycle 1 should nonetheless be recorded as the evaluation for the beginning of Cycle 2, with similar assignments for subsequent cycles).
- n. Pharmacokinetic Assessment: phase 1 only. PK samples (plasma) are to be obtained at the following time points: pre-infusion, immediately after infusion then 15, 30, 45, 60, 90, 120, 180, and 240 minutes post-infusion in Phase on Day 1 and 5 of the Run-in Cycle and Cycle 2. See table 13. Pomalidomide will be administered approximately 4-6 hours post SL-401 end of infusion for the purpose of obtaining PK samples on the day of infusion 1 and 5 of Cycle 2.
- o. Immunogenicity: Serum for immunogenicity evaluation will be collected prior to the infusion during the run-in Cycle 1 on Days 1 and 5 and on Day 1 pre-infusion at the beginning of all subsequent cycles, and at End-of-therapy. If infusions are held (postponed) for any reason, an immunogenicity sample must be collected within 3 ± 3 days after completion of the last SL-401 infusion for the cycle.
- p. Pre-medication: Approximately 60 minutes prior to each dose of SL-401, patients shall receive pre-medication with acetaminophen, diphenhydramine, methylprednisolone and ranitidine according to Section 7.3.2.2.
- q. SL-401 administration: SL-401 will be given by iv infusion over 15 minutes on Days 1 5 of each 28 day cycle (Run-in Cycle and Cycles 1 6) with delays permitted as delineated in relevant protocol sections such that administration on days 6-10 of any cycle is also permitted (5 doses may be administered over 10 days, if necessary). Dose modifications are permitted following the Run-in Cycle and Cycle 1; 5 doses of SL-401 may be administered over the initial 10 day period of each cycle. See Section 7.3.2.4 for drug administration instructions and Section 7.7 for dose modification guidelines
- r. Pomalidomide: Pomalidomide will be administered approximately 4-6 hours post SL-401 end of infusion for the purpose of obtaining SL-401 PK samples on the days of infusion 1 and 5 of Cycle 2. Pomalidomide should be taken on an empty stomach 2 hours before or after a meal. Capsules should not be opened, broken or chewed.

- s. **AE monitoring:** Patients to be observed for AEs at least 4 hours post each infusion. All AEs, including AEs of new onset as well as worsening of baseline signs and symptoms are to be reported from the signing of the informed consent to 30 days following the last administration of any study drug. After the 30 day follow-up all ongoing and new related AEs, and all the SAEs regardless of causal relationship are to be followed up to resolution or stabilization.
- t. Prior/concomitant medication should be recorded including medications taken during the 28 days prior to initial study therapy, at any/all times during study therapy/participation, and through approximately 30 days following the last dose of investigational therapy.
- u. Patients with evidence of MM stabilization or response and without unacceptable toxicity will receive the Run-in Cycle and 6 cycles of SL-401/POM/DEX. If, following completion of these cycles, there is ongoing evidence of MM stabilization or response, patients may receive additional therapy on-study if the Investigator believes the potential risk/benefit of additional therapy is justifiable. During Cycle 7 and beyond, SL-401 will be administered on Day 1-5 of every other cycle (every 56 days), POM administered on Days 1-21, and DEX administered on Days 1, 8, 15 and 22 of each cycle.
- v. EOT: Evaluations should be completed at the time a decision is made to discontinue study therapy, and approximately 30 ±7 days following the last dose of study therapy regardless for the reason of discontinuation, unless patient withdraws consent and refuses further evaluation.
- w. Follow-up: Patients who discontinue therapy for reasons other than MM progression will be followed for response every month until progression of disease or initiation of subsequent therapy. Patients who have discontinued study therapy and have had MM progression should be contacted approximately every 3 months (telephone contact is permitted) to assess overall survival status for 1 year; patients who discontinue therapy for reasons other than disease progression and are no longer willing to follow-up for evaluation of disease progression should also be contacted for survival status whenever feasible.

Table 14: Time Points for Pharmacokinetic Blood Draws

PK Blood Sample times							
Phase 1 – Run in Cycle and Cycle 2 b							
Time Point	Day 1/Infusion 1	Day 5 a/Infusion 5					
Pre-Infusion	X	X					
Immediately After End of Infusion (time recorded)	X	X					
15 Minutes Post-Infusion	X	X					
30 Minutes Post-Infusion	X	X					
45 Minutes Post-Infusion	X	X					
60 Minutes Post-Infusion	X	X					
90 Minutes Post-Infusion	X	X					
120 Minutes Post-Infusion	X	X					
180 Minutes Post-Infusion	X	X					
240 Minutes Post-Infusion	X	X					

a Day 5 may shift based on treatments held for toxicity. PK should be done on the day of the 5th infusion.

b POM and DEX to be administered 4 – 6 hours post infusion on the day of infusions 1 and 5 of Cycle 2 (POM only on Day 5). PK assessments will be performed in phase 1 only.

10 Adverse Events and Safety Evaluation

The AE reporting period for a patient treated in the study begins with the initiation of SL-401/POM/DEX and is continuous through 30 days after the last SL-401/POM/DEX dose. All AEs that occur in treated patients during the AE reporting period specified in the protocol must be reported to the Sponsor, whether or not the event is considered related to SL-401/POM/DEX. Any known untoward event that occurs beyond the AE reporting period that the Investigator assesses as related to SL-401/POM/DEX should also be reported as an AE.

All patients should be monitored per institutional guidelines for at least 4 hours following the administration of each infusion of SL-401. The Investigator, who is a physician, or medical staff responsible for study conduct and safety evaluations, should be available during the administration SL-401 and follow-up to assess, treat, or report as necessary any AE or SAE that may occur.

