Doses of SL-401 may be held for criteria specified in Section 7.7.2, Table 11, concerning abnormalities in vital signs, serum creatinine, albumin, AST/ALT or increases in body weight; in the setting of these abnormalities, 5 doses may be given over 10 days; otherwise no dose modifications are permitted during the Run-in Cycle or Cycle 1 (initial cycle of combination therapy) unless the patient experiences a DLT. No dose escalations are permitted in any given patient once a dose level has been assigned. Patients experiencing DLT during the Run-in Cycle will be discontinued from study. Patients experiencing DLT

during Cycle 1 (initial cycle of combination therapy) may continue on therapy, if toxicity can be managed according to the dose modification guidelines outlined below and the patient has not experienced disease progression; the DLT event will nonetheless contribute to the assessment of MTD for that given cohort.

Dose modifications may be performed in all subsequent cycles of treatment. If toxicities cannot be managed by dose modification or the patient cannot tolerate the lowest dose of study drug, the patient is to be discontinued from study drug unless there is evidence of disease stabilization or response beyond the initial treatment cycle. However, patients that have achieved a plateau of response to study therapy will continue to adhere to the schedule of assessments followed during the treatment phase of the study even though study drug has been discontinued.

Dose Modification Guidelines are detailed in Section 7.7.

Safety Assessments:

Safety assessments include DLTs, AEs, serious adverse events (SAEs), physical examinations, vital sign measurements, clinical laboratory evaluations, and reasons for treatment discontinuation due to toxicity. The AE reporting period for a patient treated in the study begins with the initiation of SL-401 (or SL-401/POM/DEX in phase 2) and is continuous through 30 days after the last dose of SL-401 or SL-401/POM/DEX. All AEs that occur in treated patients during the AE reporting period specified in the protocol must be reported to the Sponsor, whether or not the event is considered related to SL-401/POM/DEX. Any known untoward event that occurs beyond the AE reporting period that the Investigator assesses as related to SL-401/POM/DEX should also be reported as an AE.

Efficacy Assessments:

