4.1 Primary Objectives

- To evaluate the safety of single agent SL-401 in an initial run-in cycle in patients with MM.
- To determine the MTD or the maximum tested dose of SL-401 given in combination with POM/DEX for the treatment of relapsed or RRMM.
- To characterize the safety and tolerability profiles of SL-401 in combination with POM/DEX at the MTD.

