10.2 Period of Observation

Clinical signs and symptoms, and AEs (regardless of relationship to study drug) will be collected continuously from the first day of SL-401/POM/DEX treatment to 30 days following the last dose of SL-401/POM/DEX. All SAEs and AEs judged to be related to study drug will be collected throughout the follow-up period.

Conditions that the patient experienced prior to SL-401/POM/DEX treatment should be recorded in the patient medical history section of the eCRF. All the AEs should be followed-up at the discretion of the Investigator until the symptoms dissipate or become stable even if AEs continue beyond the period of observation. AEs unresolved at the end of the observation period will be considered "ongoing" with an undetermined outcome; however, if after the period of observation completes but prior to the completion of the study, additional outcome information becomes available, it will be reported. The severity of the signs, symptoms, or AEs should be determined using the NCI CTCAE, v.4.03. A complete CTCAE list can be downloaded at http://evs.nci.nih.gov/ftp1/CTCAE/CTCAE_4.03_2010-06-14_QuickReference_5x7.pdf.

All clinically meaningful abnormal test results should be retested. Abnormal test results that are difficult to associate with the study drug should be followed until normalized or until the abnormity could be clearly attributed to another cause. Abnormal test results should not be reported as AEs unless they meet the criteria outlined in Section 10.1.1.

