10.5 Documentation and Reporting of Adverse Events by Investigator

The Investigator is to report all directly observed AEs spontaneously reported by the patient using concise medical terminology. In addition, each patient will be questioned about AEs at each clinic visit following initiation of treatment. The question asked will be "Since your last clinic visit have you had any health problems?" or a similar question to assess health status.

The AE reporting period for this study begins upon initiation of SL-401/POM/DEX treatment and ends 30 days after the last dose of SL-401/POM/DEX. All AEs are to be reported on the AE eCRF.

All AEs that occur in study patients during the AE reporting period specified in the protocol must be reported to the Sponsor, whether or not the event is considered study drug-related. In addition, any untoward event that occurs beyond the AE reporting period that the Investigator assesses as related to the investigational product should also be reported as an AE.

Each AE is to be classified by the Investigator as serious or non-serious. This classification of the gravity of the event determines the reporting procedures to be followed. If a SAE occurs, reporting will follow local and international regulations, as appropriate. For any event that meets 1 of the SAE criteria, the Investigator must notify Medpace Clinical Safety within 24 hours of the knowledge of the occurrence. To report the SAE, complete the SAE form electronically in the electronic data capture (EDC) system for the study. When the form is completed, Medpace Safety personnel will be notified electronically and will retrieve the form. If the event meets serious criteria and it is not possible to access the internet, send an email to Medpace Safety at [contact] or call the Medpace SAE hotline (phone number listed below), and fax the completed paper SAE form to Medpace (fax number listed below) within 24 hours of awareness. When the EDC system becomes available, the SAE information must be entered within 24 hours of the system becoming available.

Safety Contact Information:

Medpace Clinical Safety

Medpace SAE hotline – USA:

[contact], [name] or [contact], [name]

[contact] or [contact]

E-mail: [contact]

Each SAE should be followed until resolution, or until such time as the Investigator determines its cause or determines that, it has become stable.

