11.1 General Considerations

Analyses will be performed on all patients that received any quantity of SL-401/POM/DEX (i.e., all treated patients). The baseline value for a given variable is defined as the last measurement for the variable prior to the first infusion of SL-401/POM/DEX. Day 1 for each individual patient is defined as the date the patient receives their first infusion of SL-401.

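### AE reporting has three conflicting start points, and the wording of Sections 10, 10.2 and 10.5, read literally, leaves out the phase 1 run-in cycle

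*Protocol*

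**What the plan says.** The first primary objective in Section 4.1 is "To evaluate the safety of single agent SL-401 in an initial run-in cycle in patients with MM". As planned, that cycle belongs to phase 1: SL-401 is given alone for one 28-day cycle, and POM and DEX are added from Cycle 1 in patients without a DLT (Section 6.2.1).

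The start of AE reporting is stated in six places and three versions:

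- **Start of the combination.** The opening of Section 10 says "The AE reporting period for a patient treated in the study begins with the initiation of SL-401/POM/DEX and is continuous through 30 days", counted from the final dose. Section 10.5 says "The AE reporting period for this study begins upon initiation of SL-401/POM/DEX treatment". Section 10.2 also collects from the first day of the three-drug treatment, and adds "Conditions that the patient experienced prior to SL-401/POM/DEX treatment should be recorded in the patient medical history section of the eCRF".
- **First SL-401.** In the synopsis (Safety Assessments) the period "begins with the initiation of SL-401 (or SL-401/POM/DEX in phase 2", so the combination start is tied to phase 2. Section 11.5 names SL-401 or the combination.
- **Informed consent.** Under note s to Table 13, all AEs "are to be reported from the signing of the informed consent to 30 days following the last administration of any study drug".

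Two related statements are also out of line. Section 11.1 says "The baseline value for a given variable is defined as the last measurement for the variable prior to the first infusion of SL-401/POM/DEX". The title of Section 9.6 is "Safety Monitoring: Through 30 days after Last Infusion", whereas other sections count from the last dose of the regimen or of any study drug.

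**The concern.** A site cannot follow three start dates. One that takes Section 10 at its word would open the AE form at Cycle 1 Day 1 and put anything from the run-in into medical history. One that follows the Section 9 visit lists and note s would report the same event as an AE. The exposure affected is the only single-agent SL-401 exposure planned, and its safety is a primary objective. If capture differs between sites, the run-in AE table will mix patients reported under different rules, and analysis cannot reliably repair that afterwards.

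**Working it through.** There is no sample size, power or alpha figure to reproduce. The check compares passages and adds some day counts.

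**1. Is the three-drug label only shorthand for any study treatment?** Four places distinguish it from SL-401 alone:
- The synopsis confines the combination start of AE reporting to phase 2.
- Sections 7.9.2 and 11.5 name SL-401 and the combination as alternatives when both are meant.
- Section 10.4 separates the pregnancy test before the first run-in dose of SL-401 from the tests before starting the combination.
- Note u to Table 13 counts the run-in cycle apart from the six cycles of the combination.

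A literal reading of Section 10 therefore fits the protocol's own usage.

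**2. Length of the gap in phase 1.** Inputs: cycle length 28 days (Section 6.2); delay before a new cycle up to 14 days, longer by exception (Section 7.8).
- No delay: 28 + 0 = 28 days from first SL-401 to first combination dose.
- Full delay: 28 + 14 = 42 days.

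The interval contains the 3 to 8 days after initiation in which Section 7.7.3.3 expects capillary leak syndrome.

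**3. Patients and exposure.** Phase 1 is 6 to 18 patients in the synopsis sample-size text and in Sections 5.1, 6.3 and 11.3. Only the synopsis item on total expected patients says 12 to 18. If each patient completes the run-in, the exposure is 6 × 28 = 168 to 18 × 28 = 504 patient-days.

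**4. Run-in days outside the AE period under each rule.**

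| Rule | Days not covered |
|---|---|
| Sections 10, 10.2, 10.5, literal | 28, up to about 42 |
| Synopsis, Section 11.5 | 0 |
| Table 13 note s | 0 |

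**5. What the literal rule does with a run-in event.** Section 10.2 sends it to medical history. Section 10.3 then does not count a pre-existing condition as an AE unless it worsens by at least one CTCAE grade. A run-in toxicity that persists unchanged into Cycle 1 could go unreported as an AE. For a patient discontinued for a run-in DLT (Section 6.2.1), the period would never open.

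**6. End of the window.** Days are counted from Day 1 of the last cycle with SL-401; the last DEX is on Day 22 of its cycle.
- Last infusion on Day 5: 5 + 30 = 35, against 22 + 30 = 52, a gap of 17 days.
- Last infusion on Day 10: 10 + 30 = 40, against 52, a gap of 12 days.
- From Cycle 7, SL-401 is given every other cycle (note u). If treatment stops after an SL-401-free cycle, the last DEX is on Day 28 + 22 = 50, and 50 + 30 = 80, against 35, a gap of 45 days.

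**7. Analysis set and baseline.** Section 11.1 analyses patients given any quantity of the three-drug regimen. The synopsis counts anyone given part of a dose of SL-401 alone, and Section 11.2.1 counts anyone given any study drug. On baseline, SL-401 is the only infused component, and the next sentence of Section 11.1 sets Day 1 at the first SL-401 infusion.

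**The case against.** The strongest reply is that the protocol plainly means to capture the run-in. The Section 9.2 visits list AE and SAE monitoring around the infusions and on Days 8, 15 and 22. The DLT period includes the run-in (Section 6.2.2). The synopsis, Section 11.5 and note s all place run-in events inside the window. Section 10.6 uses the three-drug label as the name of the investigational product, which supports reading it as shorthand, and sites work from Section 9 and Table 13 as well as from Section 10.

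Most of this stands. It shows that the intended rule includes the run-in, so one cannot say that run-in AEs are excluded. It does not remove the contradiction: three reporting sections state a different start, one of them with an explicit instruction on where earlier conditions go, and the label is not used consistently as shorthand.

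Three stronger readings are tempting, and the documents do not support them:
- A reader might infer that patients with a run-in DLT leave the analysis set. The synopsis population and Section 11.2.1 keep them in, and Section 11.2.1 counts a patient with an early DLT as evaluable for DLT.
- A reader might infer that phase 1 baselines are taken after 28 days of drug. Only SL-401 is infused, Day 1 is its first infusion, and response is assessed at the end of the run-in, which needs an earlier baseline. The wording is loose, no more.
- A reader might take 17 days as the settled shortfall in follow-up. It rests on a section title and one dosing scenario. Sections 7.9.2, 10, 10.2, 10.5 and 11.5 and note s all use the last dose.

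**Conclusion.** The AE start is wrong as written, because the protocol contradicts itself on when collection of primary safety data begins. On the literal reading of Sections 10, 10.2 and 10.5, the uncovered interval is at least 28 days, and about 42 with the standard maximum delay, in each of 6 to 18 phase 1 patients. On the other stated rules it is zero. Which applies depends on the section a site follows, so the harm is a risk of inconsistent capture and not a known loss. The size assumes the 28-day run-in and 14-day delay as stated. The analysis-set, baseline and Section 9.6 wording needs only tidying. Nothing in the sample size, power or alpha changes.

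**What to change.** - In Sections 10, 10.2 and 10.5, start the AE period and the medical-history cut-off at the first dose of any study drug: Run-in Day 1 in phase 1, Cycle 1 Day 1 in phase 2.
- Reconcile note s to Table 13 by recording events between consent and first dose as non-treatment-emergent.
- As a tidy-up, let Section 11.1 define the treated set by any study drug, as the synopsis population and Section 11.2.1 do, and place baseline before the first SL-401 infusion, matching its own Day 1.
- As a tidy-up, align the Section 9.6 title with the 30 days after the last dose of any study drug used elsewhere.

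The cost is amendment wording and a note in the case report form completion guideline.
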